**Principal Investigators: [name]**

**Background and Significance:**

Combined spinal epidural labor analgesia is a common form of labor pain relief method that provides rapid onset of labor pain relief with the first dose of medicine and also an epidural catheter is inserted for continuous administration of epidural medication throughout the duration of labor. In combined spinal epidural labor analgesia technique, an epidural is inserted first after numbing the skin with local anesthetic. When the epidural space is identified by the epidural needle, then a spinal needle is inserted through the epidural needle into the spinal fluid space. When a drop of clear spinal fluid return through the spinal needle, the spinal space is identified and then the first dose of medicine is administered through the spinal needle, after which, the spinal needle is removed and an epidural catheter is inserted into the epidural space for additional medication as needed. When the epidural needle is inserted initially to identify the epidural space, anesthesiologists typically attach to the epidural needle a syringe with 2-3 mL of air or saline. The air or saline is used to help identifying the epidural space. Both air and saline are commonly used and it is not clear and debatable which is a better method to identify the epidural space when the combined spinal epidural labor analgesia is performed. Some clinicians believe air is a better choice because when a drop of clear fluid returned from the spinal needle during the combined spinal epidural technique, it would be clear that it is from the spinal fluid since no saline and only air has been used in the syringe, and the first dose of medicine can be administered via the spinal needle. However, other clinicians believe saline is better because it allows easier and more reliable identification of the epidural space and that the saline would not interfere with the spinal fluid return from the spinal space during combined spinal epidural labor analgesia. To date, no studies have compared the outcome and success of combined spinal labor analgesia between using saline versus air for identifying the epidural space. The goal of this study is to compare whether air or saline makes a difference in success and outcomes of the combined spinal epidural labor analgesia. The results of this study may provide information on better choice of technique for obtaining combined spinal labor analgesia. A total of 350 labor patients will be enrolled at Forsyth Medical Center.

Obese patients present significant challenges for the anesthesia care providers. Neuraxial anesthesia is preferred over general anesthesia for Cesarean Section. In obese patients placement of spinal or epidural anesthesia is complicated by diminished landmarks and increased depth of the epidural and subarachnoid space. The ability to identify the epidural or subarachnoid space is more likely due to misdirection than inadequate needle length. In spinal anesthesia, a short introducer needle is used first and a spinal needle is inserted via the introducer to locate the subarachnoid space. In combined spinal epidural anesthesia technique, an epidural needle (longer than the standard introducer used in spinal anesthesia) is inserted first, and the spinal needle is inserted into the subarachnoid space via the epidural needle after epidural space is identified by the epidural needle. Both spinal and combined spinal epidural techniques are commonly used for cesarean section anesthesia. Many experienced anesthesia care providers

may have difficulty locating the spinal space with a standard short introducer and a small gauge spinal needle in obese patients and find that misdirection and time for placement of anesthesia is less when an epidural needle is used to identify tissue planes. The use of an epidural needle also allows the threading of an epidural catheter after spinal anesthesia is administered using a combined spinal epidural technique. This catheter provides additional security to the patient in the event of a prolonged operation or postoperative bleeding. To date, no studies have compared the time and success for placement of spinal anesthesia via standard spinal versus combined spinal epidural (CSE) technique in obese patients scheduled for Cesarean deliveries. The results of this study may provide anesthesia provider information on better choice of technique for obtaining subarachnoid anesthesia in obese patients undergoing cesarean deliveries.

**Purpose:**

The purpose of this study is to document the success rate and outcomes of combined spinal epidural labor analgesia when saline or air is used to identify the epidural space during the combined spinal epidural labor analgesia. Additional objectives of this study are to quantify the any complications and pain relief and satisfaction assessed by pain scores via randomized visual and verbal analog scores.

**Hypothesis:**

Use of saline in combined spinal epidural labor analgesia during identification of epidural space does not increase the failure rate of combined spinal epidural labor analgesia when compared to the use of air.

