**OUTCOME MEASURES:** The primary outcome measure will be the success or failure of the combined spinal epidural labor analgesia. Secondary outcome measures are any complication or side effects.

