#### **Statistics and Data Analysis:**

Data will be presented as mean (SD) or median as appropriate. Pain VAS scores will be examined, following tests for normality, by repeated measures two-way ANOVA in most study designs. Incidence data will be analyzed by Chi-Square or Fishers Exact Test. In the case of subject drop out, both intent to treat and completed treatment analyses will be performed. Continuous data will be compared by unpaired t-test and ANOVA. Assuming a difference in success rate of 95% versus 85% between the two groups, a sample size of 160/group is required to achieve a power of 0.8 and an alpha of 0.05. An estimate of 175/ groups or 350 total evaluable subjects will be enrolled in this study.

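### The hypothesis is that saline does not increase failure, but the trial is sized and analysed only to detect a difference, with no margin, interval or rule for a non-significant result

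*Combined protocol and SAP*

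**What the plan says.** - **Hypothesis:** saline "does not increase the failure rate of combined spinal epidural labor analgesia when compared to the use of air". This is a one-directional claim of being no worse, and it is the only hypothesis stated.
- **Outcome Measures:** "The primary outcome measure will be the success or failure of the combined spinal epidural labor analgesia". The endpoint is binary.
- **Statistics and Data Analysis, sizing:** "Assuming a difference in success rate of 95% versus 85% between the two groups, a sample size of 160/group is required" for power 0.8 and alpha 0.05, with 175 per group (350 in total) to be enrolled. It does not say which arm is expected at 95%, or whether alpha is one- or two-sided.
- **Statistics and Data Analysis, test:** "Incidence data will be analyzed by Chi-Square or Fishers Exact Test". Nothing else is planned for the primary comparison.
- **Background and Significance:** "The goal of this study is to compare whether air or saline makes a difference in success and outcomes". This is a neutral, two-sided aim. The section also records that "other clinicians believe saline is better because it allows easier and more reliable identification of the epidural space", so a benefit of saline is left open.

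No section gives a non-inferiority or equivalence margin, a confidence interval for the difference in failure, or an interpretation of a non-significant test.

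**The concern.** A claim of no increase is supported by ruling out an increase large enough to matter. That takes a margin and an interval. A test of no difference can reject equality, but failing to reject does not establish it. Under this plan the hypothesis gains support only if saline is significantly better than air. If the two media are equivalent, which makes the hypothesis true, nearly every trial ends in the one result for which the plan has no rule. The tempting reading would then be that p above 0.05 confirms the hypothesis. That leaves the primary conclusion to be settled after the data are seen, using a result that is also common when saline is harmful.

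**Working it through.** **Inputs from the documents.** Success 95% versus 85% (failure 5% versus 15%), alpha 0.05, power 0.8, 160 per group required, 175 per group enrolled, 1:1 allocation, chi-square or Fisher test.

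**Inputs assumed here.** True failure rates other than 5% and 15%, and every margin.

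**1. Reproducing the plan's figure.** With mean success 0.90 and difference d = 0.10:

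n = [1.960·√(2·0.90·0.10) + 0.842·√(0.95·0.05 + 0.85·0.15)]² / 0.10² = (0.8315 + 0.3521)² / 0.01 = 140.1, so 141.

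With continuity correction: (n/4)·[1 + √(1 + 4/(n·d))]² = (140.1/4)·(1 + 1.1338)² = 159.5, so **160**.

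The one-sided versions give 111 and 130. The stated 160 is therefore the two-sided, continuity-corrected size for detecting a difference. The arithmetic is right, but the power belongs to a superiority question.

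**2. What the planned test does at 175 per group.** The two independent binomials were enumerated exactly. The chi-square test is uncorrected.

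| True failure, saline / air | Significant favouring saline (Fisher / chi-square) | Non-significant (Fisher / chi-square) |
|---|---|---|
| 5% / 5% | 1.3% / 2.4% | 97% / 95% |
| 5% / 10% | 35% / 43% | 65% / 57% |
| 5% / 15% | 86% / 89% | 14% / 11% |
| 10% / 5% | about 0 | 65% / 57% |
| 15% / 5% | about 0 | 14% / 11% |

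**3. A single-trial example.** Take 18/175 failures with saline (10.3%) and 9/175 with air (5.1%), a difference of 5.14 points.

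- Fisher p = 0.108; chi-square = 3.25, p = 0.071.
- Wilson limits: saline 6.61% to 15.67%, air 2.73% to 9.48%.
- Newcombe lower limit: 5.14 − √[(10.29 − 6.61)² + (9.48 − 5.14)²] = −0.5 points.
- Newcombe upper limit: 5.14 + √[(15.67 − 10.29)² + (5.14 − 2.73)²] = +11.0 points.

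The test is non-significant, yet the data remain compatible with the full 10-point planning difference.

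**4. If the no-increase claim were tested directly.** The claim is made when the upper Newcombe 95% limit lies below the margin. Exact probability at 175 per group:

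| True failure, saline / air | Margin 10 points | 7.5 points | 5 points |
|---|---|---|---|
| 5% / 5% | 98% | 85% | 53% |
| 10% / 10% | 86% | 63% | 33% |
| 10% / 5% | 39% | 13% | 2% |

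Size per group for 80% power at one-sided 0.025 is (1.960 + 0.842)²·2p(1 − p)/margin². At p = 5% failure this gives 75 / 133 / 299 for margins of 10 / 7.5 / 5 points. At p = 10% it gives 142 / 252 / 566.

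**The case against.** The strongest reply is that this is an ordinary two-sided comparison with one loosely worded sentence. The Background states a neutral aim, the Purpose is to document success rates, and no section uses the language of non-inferiority. The hypothesis could be read as the null under test. On that reading the sizing and the test are coherent. The power is also relevant to refuting the hypothesis: at 15% versus 5% failure the test misses the harm in only 14% (Fisher) or 11% (chi-square) of trials. If saline were better by the plan's own 10 points, the test would show it in 86% or 89%.

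Much of this stands. The Hypothesis section is the part that does not fit. The 1.3% to 2.4% figure is simply one tail of a 5% test under equality, which any difference test would give, and it does not show that 350 is too few. The doubling from 5% to 10% is an illustrative scenario, and the worked example is not typical of trials in which the arms are equal. Nor does the plan say that a non-significant result will be read as support.

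None of this supplies the missing rule. A null that is not rejected has not been shown to be true, and the plan does not say that such a result is inconclusive. The 10-point figure cannot serve as an implied margin, because it is given as an assumed difference without direction and no interval is planned to set against it.

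**Conclusion.** The concern holds. The stated hypothesis and the planned analysis answer different questions, and the plan has no rule for the result it is most likely to obtain if the hypothesis is true. With both arms failing 5% at 175 per group, that result occurs in 97% (Fisher) or 95% (chi-square) of trials. It also occurs in 65% or 57% when saline truly doubles failure from 5% to 10%. These figures assume independent binomial outcomes, full enrolment and the stated failure rates. Whether 175 per group would suffice for a no-increase claim depends on a margin the documents do not give: at 10 points it is enough in both equal-rate scenarios shown, and at 5 points in neither. The defect must be corrected because it governs the primary conclusion, and a rule chosen after the results are known cannot repair it.

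**What to change.** **Minimum change.** Reword the Hypothesis as a two-sided question, for example that the failure rate differs between saline and air, so that it matches the Background and the sample-size calculation. In Statistics and Data Analysis, state that alpha is two-sided and make the 95% confidence interval for saline minus air failure (Newcombe or Miettinen-Nurminen) the primary result. State also that a non-significant test is inconclusive and is not evidence that saline does not increase failure. This costs wording and reporting only; sample size, randomization and data collection are unchanged.

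**If the no-increase claim is kept.** Prespecify and clinically justify a margin before unblinding, make the claim only if the upper 95% limit falls below it, and restate the power for that test. The cost depends on the margin. Under the assumed margins and failure rates above, 80% power needs from 75 to 566 per group, so some choices would require more than the planned 175. A wide margin has its own price: at 10 points the claim would still be made in 39% of trials in which failure truly doubles from 5% to 10%.

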**Patient Population:**

The patient population will consist of 350 women aged 18 years or older, weighing less than or equal to 250 lbs, and request neuraxial labor analgesia. **Emancipated minors may also be enrolled in this protocol.** Exclusion criteria will be American Society of Anesthesiologists physical status greater than II.

**Procedures and Methods:**

Demographic data including patient's age, height, weight, gestation, medications and history of previous epidurals or spinals will be recorded. Patients will be randomized into one of two treatment groups (Group Air or Group Saline) according to a table of random numbers. The patient will be placed in the sitting position and a midline approach will be used as in usual practice. Combined spinal epidural labor analgesia will be performed in the usual manner, with group Air using 3 mL of air and group Saline using 3mL of saline in the syringe for identifying the epidural space during the combined spinal epidural labor analgesia placement. After positive fluid return from the spinal needle, a standard of care acceptable usual dose of labor analgesic will be administered at the discretion of the anesthesiologist providing the care. Typically 10-20 mcg of fentanyl with or without bupivacaine 1-2.5mg will be administered. The patients and data interpreters will be blinded to the treatment group; however, the anesthesiologist performing the procedure will not be blinded. Standard of care monitoring data will be recorded as usual, and level of pain relief will be obtained via pain scores by visual and verbal pain scores.

**RANDOMIZATION AND TREATMENT:** Patients will be randomized to have the anesthesiologist using saline or air for identifying epidural space during placement of the combined spinal epidural labor analgesia using standard loss of resistance technique. The chance of using air or saline is each 50%. The patients, data interpreters and analyzers will be blinded as to which group the patient is assigned to.

**Confidentiality:** All information obtained while you are in this study, as well as related hospital records, will be made available to the research staff and other regulatory authorities including the Food and Drug Administration (FDA). All information will be treated in a confidential manner and although the results of this research project may be presented at meetings or in publications, you will only referred to by number and your identity will not be disclosed in those presentations.

**SAFETY MEASURES:** Standard monitoring will be applied in the labor room as in usual clinical practice at Forsyth Medical Center. Unless other untowards effects are observed from the techniques, no additional monitoring will not be instituted.

**OUTCOME MEASURES:** The primary outcome measure will be the success or failure of the combined spinal epidural labor analgesia. Secondary outcome measures are any complication or side effects.

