#### **Benefits and Risks:**

There may be no potential benefits from participating in this study other than more frequent assessment and observation. It is not known which technique actually provide the more favorable outcomes but both techniques are commonly used in clinical practice. The usual risks of combined spinal epidural labor analgesia include but not limited to : headache, failure of the spinal or epidural, intravenous catheter insertion and the extremely rare risks of bleeding, infection, nerve damage, paralysis, hypotension, high spinal block and even death rarely. All these risks are explained by the anesthesiologist participating or providing anesthetic care as part of the risk of neuraxial block.

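### Pain relief has a planned repeated-measures analysis, but no pre-block score and no assessment times are scheduled for it

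*Combined protocol and SAP*

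**What the plan says.** Three sections of the Combined protocol and SAP deal with pain scores.

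- Purpose lists among the additional objectives "pain relief and satisfaction assessed by pain scores via randomized visual and verbal analog scores".
- Procedures and Methods says "Standard of care monitoring data will be recorded as usual" and, in the same sentence, that "level of pain relief will be obtained via pain scores by visual and verbal pain scores". No time is given. The only pre-procedure data it names are these: "Demographic data including patient's age, height, weight, gestation, medications and history of previous epidurals or spinals will be recorded".
- Statistics and Data Analysis says "Pain VAS scores will be examined, following tests for normality, by repeated measures two-way ANOVA". It gives no time points, no baseline term and no separate rule for the verbal score.

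Background and Significance describes a spinal dose with rapid onset, after which "an epidural catheter is inserted for continuous administration of epidural medication throughout the duration of labor". It also mentions further drug through the catheter when needed. No section says when epidural drug starts. Outcome Measures names success or failure of the block as primary and complications or side effects as secondary; pain is in neither list.

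**The concern.** The air-versus-saline question turns on whether fluid seen at the spinal needle can be trusted as spinal fluid. Pain shortly after placement is therefore the informative pain measurement. If women are scored whenever it is convenient, some scores precede epidural drug and some follow it. A woman whose spinal dose failed and who was then dosed through the catheter may score the same as one whose spinal dose worked. That would pull the group difference towards zero.

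The anesthesiologist is not blinded, so unscheduled scoring also leaves room for timing to differ by arm. Relief is a change from pain at request, and without a pre-block score it cannot be measured within a woman. None of this can be recovered after enrolment.

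**Working it through.** **1. The plan's own figure.** The documents give a sample size only for success rates of 95% and 85% (power 0.8, alpha 0.05). With the pooled two-sided formula and mean rate 0.90:

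n = [1.960·√(2·0.90·0.10) + 0.8416·√(0.95·0.05 + 0.85·0.15)]² / 0.10² = (0.8315 + 0.3521)² / 0.01 = 140.1, or 141.

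With continuity correction: (140.1/4)·[1 + √(1 + 4/(140.1·0.10))]² = 159.5, or 160. The stated 160 per group reproduces. It does not depend on pain scores.

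**2. What the pain analysis needs, against what is scheduled.**

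| Needed | In the plan |
|---|---|
| Common times for a repeated-measures ANOVA | None stated |
| A time relative to epidural drug | None stated; start of epidural drug not stated |
| A pre-block score, if relief is to be measured | Not among the pre-procedure data named |
| One scale held by every woman | Visual and verbal collected; only VAS clearly named for analysis |

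**3. Possible dilution (illustration).** Failure rates of 15% and 5% are the complements of the plan's success rates. Three things are assumed: mean pain of 6 after a failed spinal and 1 after a working one (0–10 scale), and that every failure is a failed spinal dose.

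- Soon after placement: 0.15·6 + 0.85·1 = 1.75; 0.05·6 + 0.95·1 = 1.25; difference 0.50.
- In general, the difference is 0.10 × (gap between failed and working scores) × (1 − f), where f is the share of failures already relieved through the catheter. With a gap of 5 it runs from 0.50 at f = 0 to 0 at f = 1. Each point of gap is worth 0.10 at f = 0.

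The documents do not give f. It depends on when scores are taken and when epidural drug starts.

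**4. Cost of having no baseline.** A baseline covariate with correlation r to the outcome leaves 1 − r² of the residual variance. The values of r are assumed.

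- r = 0.3: 0.91, a 9% reduction.
- r = 0.5: 0.75, a 25% reduction.

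Without a baseline, 175 per group detects a standardised difference of (1.960 + 0.8416)·√(2/175) = 0.30 at 80% power. With it, this becomes 0.30·√0.91 = 0.29 or 0.30·√0.75 = 0.26. Equivalently, 175 women carry the information of 175/0.91 = 192 or 175/0.75 = 233.

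A simple change score would not give this gain. With equal variances its variance is 2(1 − r) times that of the post-block score: 1.4 at r = 0.3 and 1.0 at r = 0.5. The baseline should therefore enter as a covariate.

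**5. Scale wording.** Purpose speaks of "pain scores via randomized visual and verbal analog scores", Procedures and Methods of both scales with no randomisation between them, and the analysis section of VAS. The three do not describe the same data.

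**The case against.** **Pain is not a listed outcome.** It is absent from Outcome Measures, and the hypothesis and sample size rest on failure or success of the block. A failed block counts in the primary outcome whatever later pain scores show. This stands and limits the point to a supporting analysis. That success itself is undefined is a larger, separate gap.

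**Well-timed pain scores would still be the weaker detector of failure.** Using the scores above and an assumed within-state SD of 1, the two group variances are 1 + 0.15·0.85·25 = 4.19 and 1 + 0.05·0.95·25 = 2.19. The standard error at 175 per group is √(6.375/175) = 0.19, and power for 0.5 is about 0.75. With an SD of 2 it is about 0.47. The primary comparison has about 0.88. This stands too.

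**A baseline may be intended.** The pre-procedure list is open-ended and headed as demographic, and repeated measures could include a pre-block score. That is possible, but none is written down. Randomisation keeps the comparison unbiased without one.

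**A reader might infer that the pain data cannot show whether the spinal dose worked.** The documents do not support this. They do not say that scores are taken only after epidural drug starts, and they never assign the pain scores that task. Dilution is a risk of unset timing, not a certainty.

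**A reader might infer that power for a 0.3 SD difference falls from 0.80 to 0.51**, with about 87 instead of 175 women per group supplying a VAS. That needs the single word randomized in Purpose to mean one scale per woman, whereas Procedures and Methods collects both. If time points were randomised, every woman could still contribute. Nor is it established that the verbal score goes unanalysed: the general sentence on continuous data could cover it, and VAS could be read as verbal analog score.

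**A reader might see a contradiction with Benefits and Risks**, where the only benefit is "other than more frequent assessment and observation". The added pain scores may be exactly that, so no conflict is shown.

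**Conclusion.** The point holds as a cheap improvement to a supporting analysis. As written, the plan gives no common times for its repeated-measures ANOVA, no anchor separating the spinal dose from epidural drug, and no pre-block score.

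Two effects should be kept apart. Unset timing can dilute the group difference: in the illustration by anything from none to all of 0.5 points, resting on assumed scores of 6 and 1 and on treating every failure as a failed spinal dose. The missing baseline costs precision only: 9% to 25% of residual variance at assumed correlations of 0.3 to 0.5. The scale wording needs reconciling, but no power loss can be attached to it. The primary comparison and its 160 per group stand.

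**What to change.** 1. In Procedures and Methods, record one pain score just before the block. In Statistics and Data Analysis, enter it as a covariate in the pain analysis.
2. Score every randomised woman at the same prespecified early times, counted from a point every woman has, such as the end of block placement. The spinal dose will not serve, because it is given only after fluid return and some women may never receive it. Record when epidural drug starts.
3. Keep all randomised women in the comparison, and state in advance how those given epidural drug, or no spinal dose, before a scheduled score are counted (for example as not relieved, with the score or category this implies written down). Do not limit the analysis to scores before epidural drug. That conditions on a post-randomisation event, would selectively remove failures, and would undercut the planned intent-to-treat analysis.
4. Reconcile the scale wording in Purpose, Procedures and Methods, and Statistics and Data Analysis, so that the scale analysed is collected from every woman at every time.

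The cost is a few more bedside scores per woman and some protocol wording. No treatment and no sample size changes, but the edits must be in place before enrolment.
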